5.6 Withdrawal of Subjects

Subjects are encouraged to complete all study evaluations. However, they may withdraw from the study at any time and for any reason. Every effort will be made to determine why any subject withdraws from the study prematurely. All subjects who withdraw from the study with an ongoing AE must be followed until the event is resolved or deemed stable. At the time that a subject withdraws prematurely for any reason, all assessments as listed for the EOS visit should be performed. If a subject withdraws prematurely after dosing, all data to be collected prior to discharge from the clinical site will be collected at the time of premature discontinuation or at the scheduled end-of-study visit. Subject participation may be terminated prior to completing the study and the reason recorded as follows:

1. Adverse event
2. Protocol violation

3. Loss to Follow-up
4. Subject withdrew consent
5. Investigator withdrew subject to give rescue therapy other than steroids
6. Other

A comprehensive effort must be made to determine the reason(s) why a subject fails to return for the necessary visits or is discontinued from the study. If the subject is unreachable by telephone, a registered letter, at minimum, should be sent to the subject requesting him/her to contact the study site.

Subjects withdrawn due to AEs considered to have a possible relationship to study drug will not be replaced. Subjects withdrawn for a non-drug related reason will be replaced if deemed necessary by the Sponsor. The decision regarding the replacement of subjects will be documented.

If a subject withdraws prematurely, all assessments as listed for the EOS visit should be performed and recorded on an unscheduled visit eCRF page. In addition, the subject should be scheduled for a follow-up visit 4 weeks from the time of the last injection of study drug, at which time all assessments as listed for the EOS visit should be performed.

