 - a. Symptom Severity Index
 - b. Glucocorticoid Toxicity Index
 - c. SF-36 Health Survey
 - d. Patient Global Activity VAS
9. Physician-reported outcomes
 - a. Glucocorticoid Toxicity Index
 - b. Physician global activity VAS
 - c. IgG4-RD RI
10. Study drug administration and teaching
11. Study medication dispense

Visit 3 (week 4)-visit 10 (week 36)

Patients will have visits at Weeks 4, 8, 12, and then every 4 weeks per the schedule of assessments shown in Table 1

1. Brief physical exam including vital signs (Full physical exam at EOS)
2. Assessment of signs and symptoms of IgG4-RD
3. Concomitant Medications review
4. Adverse Events Assessments
5. Assessment of signs and symptoms of IgG4-RD activity
6. Abatacept administration (baseline, w4, w12, w20, w28, w36, w44)
7. Laboratory tests (to be drawn before study product administration). See schedule of events.
 - i. Mechanistic samples will be collected from subject at weeks 0, 1, 4, 12 and 24 studies)
8. Patient-reported outcomes (per schedule of events, table 1)
9. Physician reported outcomes (per schedule of events, table 1)
10. Study medication accountability and dispense

Safety follow up visit (if needed)

During the safety follow up the following procedures will be completed

1. Vital signs and Physical exam
2. Concomitant Medications review

3. Adverse Events Assessments
4. Assessment of signs and symptoms of IgG4-RD

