6.9 Contraception

- Women of childbearing potential must have a negative pregnancy test during screening and at baseline (Day 1) and must use 1 highly effective method of birth control during the study and for 3 months following the last dose of abatacept. Highly effective methods of birth control include hormonal birth control, intrauterine devices (IUDs), or any barrier methods (sponges, female condoms) used by the woman in addition to contraception used by their male partner such as a vasectomy or a condom supplemented with spermicide.
- Women of non-childbearing potential must have a documented reason (i.e., postmenopausal by history with no menses for one year and confirmed by FSH [using local reference ranges], OR history of hysterectomy, OR history of bilateral tubal ligation, OR history of bilateral oophorectomy).
- Male subjects of childbearing potential must be willing to practice a highly effective method of birth control for the duration of the study and continuing for 3 months after the last dose of abatacept. Highly effective methods of birth control include a vasectomy or a condom in combination with barrier methods, hormonal birth control or IUD used by the woman.

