7.3 POST- STUDY ACCESS & ADVERSE EVENT REPORTING INFORMATION FOR INTERVENTIONAL PROTOCOLS

At the end of the study period, Bristol-Myers Squibb Company will not continue to supply study drug to subjects/investigators unless the Sponsor-Investigator chooses to extend their study. The investigator is responsible to ensure that the subject receives appropriate standard of care or other appropriate treatment in the independent medical judgement of the Investigator to treat the condition under study.

- All Serious Adverse Events (SAEs) that occur following the subject's written consent to participate in the study through 30 days of discontinuation of dosing must be reported to BMS Worldwide Safety, whether related or not related to study drug. If applicable, SAEs must be collected that relate to any later protocol-specified procedure (eg, a follow-up skin biopsy).
- Following the subject's written consent to participate in the study, all SAEs, whether related or not related to study drug, are collected, including those thought to be associated with protocol-specified procedures. The investigator should report any SAE occurring after these aforementioned time periods, which is believed to be related to study drug or protocol-specified procedure.
- An SAE report should be completed for any event where doubt exists regarding its seriousness;
- If the investigator believes that an SAE is not related to study drug, but is potentially related to the conditions of the study (such as withdrawal of previous therapy or a complication of a study procedure), the relationship should be specified in the narrative section of the SAE Report Form.
- If the BMS safety address is not included in the protocol document (eg, multicenter studies where events are reported centrally), the procedure for safety reporting must be reviewed/approved by the BMS Protocol Manager. Procedures for such reporting must be reviewed and approved by BMS prior to study activation.

An appropriate SAE form (e.g. ex-US = CIOMS form or USA = Medwatch form) will be used to report SAEs to BMS.

- The CIOMS form is available at: <http://www.cioms.ch/index.php/cioms-form-i>
- The MedWatch form is available at: [MedWatch 3500 Form](#)
- For studies with long-term follow-up periods in which safety data are being reported, include the timing of SAE collection.

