Adverse events can be spontaneously reported or elicited during open-ended questioning, examination, or evaluation of a subject. (In order to prevent reporting bias, subjects should not be questioned regarding the specific occurrence of one or more AEs.)

NONSERIOUS ADVERSE EVENT

- Non-serious Adverse Events (AE) are to be provided to BMS in aggregate via interim or final study reports as specified in the agreement or, if a regulatory requirement [eg, IND US trial] as part of an annual reporting requirement.
- Non-serious AE information should also be collected from the start of a placebo lead-in period or other observational period intended to establish a baseline status for the subjects.

A *non-serious adverse event* is an AE not classified as serious.

Non-serious Adverse Event Collection and Reporting

The collection of non-serious AE information should begin at initiation of study drug. All non-serious adverse events (not only those deemed to be treatment-related) should be collected continuously during the treatment period and for a minimum of 30 days following the last dose of study treatment.

Non-serious AEs should be followed to resolution or stabilization, or reported as SAEs if they become serious. Follow-up is also required for non-serious AEs that cause interruption or discontinuation of study drug and for those present at the end of study treatment as appropriate.

Laboratory Test Abnormalities

All laboratory test results captured as part of the study should be recorded following institutional procedures. Test results that constitute SAEs should be documented and reported to BMS as such.

The following laboratory abnormalities should be documented and reported appropriately:

- any laboratory test result that is clinically significant or meets the definition of an SAE
- any laboratory abnormality that required the participant to have study drug discontinued or interrupted
- any laboratory abnormality that required the subject to receive specific corrective therapy.

It is expected that wherever possible, the clinical rather than laboratory term would be used by the reporting investigator (eg, anemia versus low hemoglobin value).

Potential Drug Induced Liver Injury (DILI)

Potential drug induced liver injury is defined as:

- 1) AT (ALT or AST) elevation > 3 times upper limit of normal (ULN)

AND

- 2) Total bilirubin > 2 times ULN, without initial findings of cholestasis (elevated serum alkaline phosphatase)

AND

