- 3) No other immediately apparent possible causes of AT elevation and hyperbilirubinemia, including, but not limited to, viral hepatitis, pre-existing chronic or acute liver disease, or the administration of other drug(s) known to be hepatotoxic.

Wherever possible, timely confirmation of initial liver-related laboratory abnormalities should occur prior to the reporting of a potential DILI event. All occurrences of potential DILIs, meeting the defined criteria, must be reported as SAEs.

Pregnancy

If, following initiation of the investigational product, it is subsequently discovered that a study participant is pregnant or may have been pregnant at the time of investigational product exposure, including during at least 5 half-lives after product administration, the investigational product will be permanently discontinued in an appropriate manner (eg, dose tapering if necessary for participant).

The investigator must immediately notify [contact] of this event via either the CIOMS, MedWatch or appropriate Pregnancy Surveillance Form in accordance with SAE reporting procedures.

Protocol-required procedures for study discontinuation and follow-up must be performed on the participant.

Follow-up information regarding the course of the pregnancy, including perinatal and neonatal outcome and, where applicable, offspring information must be reported on the CIOMS, MedWatch, BMS Pregnancy Surveillance Form, or approved site SAE form. A BMS Pregnancy Surveillance Form may be provided upon request.

Any pregnancy that occurs in a female partner of a male study participant should be reported to BMS. Information on this pregnancy will be collected on the Pregnancy Surveillance Form. In order for

Sponsor or designee to collect any pregnancy surveillance information from the female partner, the female partner must sign an informed consent form for disclosure of this information.

Overdose

An overdose is defined as the accidental or intentional administration of any dose of a product that is considered both excessive and medically important. All occurrences of overdose must be reported as an SAE.

Other Safety Considerations

Any significant worsening noted during interim or final physical examinations, electrocardiograms, X-rays, and any other potential safety assessments, whether or not these procedures are required by the protocol, should also be recorded as a non-serious or serious AE, as appropriate, and reported accordingly.

Laboratory Assessments

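### Section 5.6 schedules no contact after day 28 off drug for subjects who withdraw within 28 days of their last injection, so new events after that day are not actively sought

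*Protocol*

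**What the plan says.** **Early withdrawals.** Protocol section 5.6 requires the end-of-study assessments at the time of withdrawal and, in addition, that "the subject should be scheduled for a follow-up visit 4 weeks from the time of the last injection of study drug". Another sentence there, about data due before a subject is discharged from the site, says that such data "will be collected at the time of premature discontinuation or at the scheduled end-of-study visit". Subjects with an ongoing adverse event are followed until it resolves or is stable.

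**Collection windows.** Section 7.3 requires that serious events "through 30 days of discontinuation of dosing must be reported to BMS Worldwide Safety". Non-serious events are to be collected during treatment and "for a minimum of 30 days following the last dose of study treatment". Beyond these windows, "The investigator should report any SAE occurring after these aforementioned time periods, which is believed to be related to study drug". Footnote 4 to the schedule in section 5.1 lets site staff collect events and concomitant medication by phone or email. Section 5.2 also lists a safety follow-up visit, to be used only if needed and with no fixed time.

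**Completers.** The description in section 5 follows them for 12 weeks after the last dose, with visits at weeks 28 and 36. The schedule in section 5.1 marks adverse events, concomitant medication and a pregnancy test at both visits.

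**Who leaves early.** Section 5.8 stops subjects for a possibly drug-related serious or significant non-serious event when the investigator or the sponsor's medical representative judges this warranted. The description in section 5 ends the study for those who need rituximab or another added oral immunosuppressant. Subjects rescued with steroids may stay.

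**Related periods.** Under section 6.9, women of childbearing potential "must use 1 highly effective method of birth control during the study and for 3 months following the last dose of abatacept"; a 3-month period also applies to men. The pregnancy text in section 7.3 counts exposure as "including during at least 5 half-lives after product administration".

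**The concern.** The 4-week visit stops short of the protocol's own 30-day window and well short of the follow-up that completers receive. The subjects affected include those for whom late safety information matters most: people taken off abatacept for a possible drug reaction, and people who start a second immunosuppressant soon after it. A new infection or pregnancy in the third month off drug would be asked about at a planned visit in a subject who tolerated 24 weeks of dosing. In an early stopper, nobody is scheduled to ask.

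The listed safeguards do not do that job. Following an ongoing event does not uncover a new one. Reporting a later related serious event presupposes that the site hears of it, and leaves out later non-serious events. Phone or email is a method with no date attached for early withdrawals. With about 10 subjects, and with serious events, deaths and discontinuations due to adverse events listed individually (section 8.2), one unrecorded event could alter the safety account.

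**Working it through.** All times are in days from the last injection.

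**Inputs**
- Post-withdrawal visit, section 5.6: 4 × 7 = 28.
- Minimum collection window, section 7.3: 30.
- Completers' last visit, section 5: week 36; last dose at week 24 (sections 5 and 5.1).
- Contraception period, section 6.9: 3 months, or 89 to 92 days by calendar.

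**The plan's own figure.** (36 − 24) × 7 = 84 days = 12 weeks. The stated 12-week follow-up is reproduced.

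**Last scheduled contact.** A subject who withdraws d days after the last injection is assessed on day d and again on day 28, so the last scheduled contact is day max(28, d).

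| Withdrawal day d | Last scheduled contact | Shortfall against day 30 | Gap to day 84 |
|---|---|---|---|
| 0 to 28 | 28 | 30 − 28 = 2 | 84 − 28 = 56 |
| 42 (week 30) | 42 | 0 | 84 − 42 = 42 |
| 84 (week 36) | 84 | 0 | 0 |

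The full gap therefore applies to any withdrawal during weekly dosing or in the first 28 days off drug, and shrinks after that.

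**Sensitivity to the last dose.** Section 3.3 mentions 25 doses where the rest of the protocol has 24. If the last dose fell at week 23, completers would be followed to day 91 and the gap would be 63 days. If it fell at week 25, they would be followed to day 77 and the gap would be 49 days.

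**Contraception period, for context.** Day 28 falls 89 − 28 = 61 to 92 − 28 = 64 days before its end. The completers' last test falls 89 − 84 = 5 to 92 − 84 = 8 days before its end.

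**Scale (assumed).** The protocol gives no withdrawal rate. Suppose k of 10 subjects stop with d up to 28. The off-drug days with no later scheduled contact are 56k out of 10 × 84 = 840: 0% for k = 0, 6.7% for k = 1, 13.3% for k = 2 and 20.0% for k = 3.

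**Is a later contact scheduled elsewhere?** The nearest candidate is the reference in section 5.6 to the scheduled end-of-study visit. It offers an alternative time for data due before discharge and does not clearly bring early withdrawals back at week 36. Collecting events until study termination (section 5) does not help when the subject's termination is itself early.

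**The case against.** The case for leaving the text alone is substantial.

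- **The 2 days.** A reader might infer that events on days 29 and 30 are lost, or that section 5.6 contradicts section 7.3. The documents do not support that. The duty to collect to day 30 is tied to no clinic visit and can be met by phone or email. Completers also have their first off-drug visit on day 28. This is a mismatch in scheduling only. The objection stands.
- **Contraception and half-lives.** A reader might infer that a required pregnancy surveillance period is cut short. Section 6.9 places a duty on the subject and does not oblige the site to test until it ends; the completers' last test also falls short of it. The half-life clause says what to do once a pregnancy is discovered, and the protocol gives no half-life. Neither rule is breached. The objection stands.
- **The 12-week comparison.** Week 36 is an efficacy time point, and no text makes 84 days off drug a safety standard. This stands as a limit: 56 days is a difference in surveillance between two groups of subjects, not a missed requirement.
- **Who gains.** Subjects with an ongoing event stay in contact with the site, and those who withdraw consent or are lost gain nothing. That narrows the group to consenting subjects whose event has resolved, those switched to another immunosuppressant, and a few others. It does not empty it.

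What the objection does not supply is any scheduled contact after day 28 intended to find a new event in those subjects.

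**Conclusion.** The point holds as a small, inexpensive improvement in safety follow-up. For subjects who withdraw within 28 days of the last injection, the last scheduled contact is day 28: 2 days before the 30-day minimum ends and, with the last dose at week 24, 56 days before the completers' last check.

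Two further inferences should be resisted. The first is that this describes most withdrawals, or a known share of follow-up time. The protocol gives no withdrawal rate, and the 0% to 20.0% range rests wholly on assuming 0 to 3 early stoppers. The second is that the safety results would be biased. There is no comparator arm. If treatment-emergent events are cut off at 30 days, only days 29 and 30 are at issue and collection already covers them. If the cut-off runs to the end of study, days 29 to 84 are at issue. The protocol does not give that cut-off, and it may properly be left to the analysis plan. Efficacy results are unaffected.

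**What to change.** Amend section 5.6 in two places.

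1. Hold the post-withdrawal visit 30 to 35 days after the last injection, or keep it at 4 weeks and add a call on day 30 or later.
2. Add one phone or email contact at about 13 weeks (day 91 to 92) after the last injection for early stoppers who consent. It should cover new adverse events, pregnancy and concomitant medication, including the start date of any new immunosuppressant. A contact at 12 weeks would match completers but would end 5 to 8 days before the contraception period does; 13 weeks (13 × 7 = 91 days) reaches about its end.

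**Cost.** One extra remote contact per consenting early stopper, or two if the day-28 visit is kept. With 0 to 3 early stoppers assumed, that is 0 to 3 contacts, or 0 to 6. Moving the visit delays the off-drug laboratory tests by 30 − 28 = 2 to 35 − 28 = 7 days; keeping it and adding the call avoids the delay. Events after a switch to another immunosuppressant will be confounded with the new drug. That limits attribution but not capture, which is why its start date should be recorded. No new in-person procedure is needed.

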5.7 Other Subject Restrictions

Subjects must have signed and dated an IRB/IEC-approved written informed consent form in accordance with regulatory and institutional guidelines before the performance of any protocol-related procedures. Prisoners or subjects who are compulsory detained will not be eligible to participate.

5.8 Stopping Criteria for the Clinical Study

Participation for any individual subject will be stopped if the subject experiences a possibly drug-related SAE or a possibly drug-related significant non-serious AE, which in the opinion of the PI or Sponsor's medical representative, warrants discontinuation of the subject in the study in the interest of that subject's well-being. Discontinuation of the subject from the study will be discussed with the Sponsor.

The Investigator will make all appropriate safety assessments on an ongoing basis. The Sponsor's medical representative will review individual safety information as it becomes available throughout the study.

An IDMC will be used to evaluate interim safety and efficacy results and to determine if the trial should be stopped early. All unblinded analyses for IDMC review will be prepared by an independent Data Coordinating Center (IDCC). Members of the IDMC will be external to the Sponsor's study team and will follow a charter that outlines their roles and responsibilities. Prior to the planned interim analyses of the primary endpoint, the IDMC will meet approximately twice annually to review safety.

6. TREATMENT OF SUBJECTS

6.1 Identity of Study Treatment(s)

ORENCIA (abatacept) is a soluble fusion protein that consists of the extracellular domain of human cytotoxic T-lymphocyte-associated antigen 4 (CTLA-4) linked to the modified Fc (hinge, CH2, and CH3 domains) portion of human immunoglobulin G1 (IgG1). Abatacept is produced by recombinant DNA technology in a mammalian cell expression system. The apparent molecular weight of abatacept is 92 kilodaltons.

ORENCIA solution for subcutaneous administration is supplied as a sterile, preservative-free, clear, colorless to pale-yellow solution with a pH of 6.8 to 7.4. Each single dose of subcutaneous injection provides 125 mg abatacept, dibasic sodium phosphate anhydrous (0.838 mg), monobasic sodium phosphate monohydrate (0.286 mg), poloxamer 188 (8 mg), sucrose (170 mg), and quantity sufficient to 1 mL with water for injection. Unlike the intravenous formulation, ORENCIA solution for subcutaneous administration contains no maltose.

Active substance: abatacept

Tested indication: IgG4-RD

Strength: 125.0 mg/syringe

Dosage form: prefilled glass syringe

Route of administration: SC injection

The dosing and schedule are supported by Phase I or later research.

6.2 Administration of Study Treatment(s)

All subjects will receive abatacept.

6.3 Treatment Protocol

- **Abatacept (Orencia)**: One 125 mg/mL single-dose prefilled glass syringe will be administered by subcutaneous (SC) injection weekly by the patients or caregivers. Patients and caregivers will be trained on how to administer the medication by the study investigators or a designated study staff member during baseline and week 1 visits. Abatacept interruptions or withdrawals will be as per the current U.S. product insert (See Attached Package Insert).

- **Prednisone taper**: Subjects who are on prednisone at baseline will begin an investigator-directed corticosteroid taper designed to discontinue prednisone not later than 8 weeks after the baseline visit.

